7.4.1.7 Infusion Interruption

The number and percentage of subjects with any interruption in their elotuzumab infusion, with 1, 2, 3, or ≥ 4 interruptions, with an interruption due to "infusion reaction", "infusion administration issues" and "other" will be presented. In addition, duration of interruptions (in minutes) will be summarized via descriptive statistics.

A subject listing will be generated for elotuzumab IV interruptions. This listing will include reason for interruption, whether the interruption was resumed, and duration of the interruption.

The number and percentage of subjects with any elotuzumab IV rate reduction, with 1, 2, 3, or ≥ 4 rate reductions, and with rate reductions due to "infusion reaction," "infusion administration issues," and "other" will be presented.

A listing will be generated for elotuzumab IV rate reductions.

7.4.1.8 *Pomalidomide*

The number and percentage of subjects with a dose reduction, omission and discontinuation which will be collected on the records from the dosing CRF page.

Reduction of Pomalidomide will also be computed based on the actual dose received. In any study day (excluding, cycle 1, day 1), the drug will have a calculated reduction compared to the

previous day, if the actual level of the administered dose is below the actual level of the administered dose in the previous instance. The information for this analysis will be derived programmatically, using

the total daily dose on the "Record of Study Medication - pomalidomide" eCRF page. The daily dose levels are defined as follows:

- Dose level 0 or full dose (4mg)
- Dose level -1 (3mg)
- Dose level -2 (2mg)
- Dose level -3 (1mg)

The number and percentage of subjects with a dose reduction, and the lowest dose level achieved per subject (-1, -2, -3), will be presented.

The reason for dose reduction as reported by the investigator will be tabulated for all instances with a calculated reduction based on the dose modification for Pomalidomide page. A category "unknown" will be defined for all calculated reductions with no reason reported by the investigator.

The number of subjects with any reported dose changes including reduction, omission and discontinuation, with 1, 2, 3, or ≥ 4 reported dose changes will be provided. The reason for dose changes (from the dose modification page of the CRF) will be summarized in the groups: "hematologic toxicity", "non-hematologic toxicity", "AE", "dosing error" and "other". For subjects without an available reason for omission, the category "unknown" will be used.

A by-subject listing of dose reductions will be generated. This will include all reported reductions per investigator, regardless of whether it met the requirements for a calculated reduction

7.4.1.9 Dexamethasone (Oral)

For PO dexamethasone the following summaries will be produced:

- The number of subjects with any dose modification, and with a reason for the modification of "hematologic toxicity", "non-hematologic toxicity", "AE", "dosing error" and "other").
- The total number of modifications of the drug experienced by a subject, both overall and by the reason for the modification.

By subject listings of record of study medication for each of IV dexamethasone and PO dexamethasone will be provided.

7.4.1.10 Cumulative Dose, Dose Intensity, and Relative Dose Intensity

A subject's cumulative dose of elotuzumab is measured in mg/kg, and is defined as the sum of their elotuzumab doses (mg/kg) (actual, not planned) over all infusions. Most recent weight will be used for the calculation. A subject's cumulative dose of pomalidomide is defined as the sum of each dose they took, as recorded in their medication diary. In order to compute the cumulative dose of dexamethasone however, IV dexamethasone will have to be converted to its equivalent oral dose. This will be done by treating each mg of IV dexamethasone as 1.32mg of oral dexamethasone, i.e. making use of the fact that the mean bioavailability of oral dexamethasone

was estimated to be 0.76^{19} . A subject's cumulative dose of dexamethasone will be defined as the sum of all dexamethasone doses, oral and IV, converted to oral equivalent. The cumulative dose administered will be summarized for each of these drugs.

Elotuzumab:

Elotuzumab dose intensity (mg/kg/week) per subject will be calculated separately for Cycles 1 and 2, and Cycle 3 and beyond, since elotuzumab dosing in Cycles 1 and 2, and Cycle 3 and beyond differ from each other.

Cycle 1 and 2:

7x[cumulative dose of Elotuzumab during the first 2 cycles/ (min(date of first dose of Elotuzumab in the last cycle among the first 2 cycles+28, discontinuation date, death date) - date of first dose of Elotuzumab in cycle 1)]

Cycle 3 and beyond:

7x[cumulative dose of Elotuzumab staring from Cycle 3 / (min(date of first dose of Elotuzumab in the last cycle+28, discontinuation date, death date) - date of first dose of Elotuzumab in cycle 3)]

The relative dose intensity will be calculated as

(Dose Intensity/Planned Dose Intensity(PDI))×100%

Planned dose per week for elotuzumab is 10mg/kg/week for the first 2 cycles, 5mg/kg/week for cycles 3 and beyond. The PDI per subject for elotuzumab will be computed by averaging the planned doses per week over the treatment duration e.g., planned elotuzumab PDI for a subject whose last dose was the first dose of third cycle would have the PDI computed as

Elotuzumab PDI ((mg/kg/wk) =
$$\frac{4 \times 10 + 4 \times 10 + 4 \times 5}{12}$$

Dose intensity and relative dose intensity of elotuzumab will be summarized.

Pomalidomide:

Dose intensity and relative dose intensity for pomalidomide (mg/week) will be calculated as the standard daily dose, 4 mg from Day 1 to Day 21 during each cycle.

The pomalidomide dose intensity, per subject, will be calculated as:

7x[cumulative dose of pomalidomide / (min(date of first dose of Pomalidomide in the last cycle in which Pomalidomide was administered+28, discontinuation date, death date) - date of first dose of Pomalidomide)]

The relative dose intensity of pomalidomide is the dose intensity per week divided by the planned dose intensity per week, 21mg times 100%.

Dexamethasone:

The dose intensity (mg/week) of dexamethasone, per subject, will be calculated separately for the period encompassing Cycles 1 and 2 and for the periods from Cycles 3 and beyond.

Cycle 1 and 2:

7x[cumulative dose of Dexamethasone during the first 2 cycles/ (min(date of first dose of Dexamethasone in the last cycle among the first 2 cycles+28, discontinuation date, death date) - date of first dose of Dexamethasone in cycle 1)]

Cycle 3 and beyond:

7x[cumulative dose of Dexamethasone staring from Cycle 3 / (min(date of first dose of Dexamethasone in the last cycle+28, discontinuation date, death date) - date of first dose of Dexamethasone in cycle 3)]

Age	Day	1	8	15	22
Cycles 1 and 2			•		
\leq 75 years old	Dexamethasone	28 mg PO +			
	(mg)	8 mg IV ^{a,b}			
> 75 years old	Dexamethasone	8 mg PO +			
	(mg)	8 mg IV ^{a,b}			
Cycles 3 and bey	ond				
≤ 75 years old	Dexamethasone	28 mg PO +	40 mg PO per	40 mg PO per	40 mg PO per
	(mg)	8 mg IV ^{a,b}	week ^c	week ^c	week ^c
> 75 years old	Dexamethasone	8 mg PO +	20 mg PO per	20 mg PO per	20 mg PO per
	(mg)	8 mg IV ^{a,b}	week ^c	week ^c	week ^c

Table 3: Dexamethasone Dosing, All Subjects Receiving Elotuzumab

^a On days of elotuzumab, infusion dexamethasone will be administered as a split dose of:

28 mg PO, for subjects \leq 75 years old or 8 mg PO for subjects > 75 years old (between 3 - 24 hours before the start of elotuzumab infusion)

AND

8 mg IV (on the day of elotuzumab infusion at least 45 minutes before the start of infusion)

^b If elotuzumab dosing is skipped or discontinued, dexamethasone will be administered orally as in days without elotuzumab.

^c Note the dexamethasone dose, as elotuzumab is not given on Days 8, 15 and 22 of cycle 3 and beyond.

The relative dose intensity of dexamethasone is the dose intensity per week divided by the planned dose intensity per week times 100%. The planned dose of dexamethasone (indicated in table 3) on elotuzumab dosing days, 8 mg IV dexamethasone plus 28 mg oral dexamethasone, is equivalent to 38.56 mg of oral dexamethasone for subjects \leq 75 years old; similarly for subjects

> 75 years old, the planned dose on elotuzumab dosing days, 8 mg IV dexamethasone plus 8 mg oral dexamethasone, is equivalent to 18.56 mg of oral dexamethasone. The planned dose when dexamethasone is not being administered with elotuzumab is 40 mg per week for subjects \leq 75 years old and 20 mg per week for subjects > 75 years old.

Nivolumab:

The dose intensity (mg/week) of Nivolumab, per subject, will be calculated separately for the period encompassing Cycles 1 to 4 and for the periods from Cycles 5 and beyond.

Cycle 1-4:

7x[cumulative dose of Nivolumab during the first 4 cycles/ (min(date of first dose of Nivolumab in the last cycle among the first 4 cycles+28, discontinuation date, death date) - date of first dose of Nivolumab in cycle 1)]

Cycle 5 and beyond:

7x[cumulative dose of Nivolumab staring from Cycle 5 / (min(date of first dose of Nivolumab in the last cycle+28, discontinuation date, death date) - date of first dose of Nivolumab in cycle 5)]

The relative dose intensity of nivolumab is the dose intensity per week divided by the planned dose intensity per week, 120mg times 100%.

Descriptive statistics (n, mean, STD, median, min, max, q1 and q3) will be presented for the cumulative dose, and dose intensity of each agent. The number and percentage of subjects whose relative dose intensity falls into the following categories will be presented: \geq 90 %, 80% to < 90%, 70% to < 80%, 60% to < 70%, < 60%.

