4.5.8 Dose Delay, Interruption, or Discontinuation for All Subjects

Please refer to Sections 4.5.8.1, 4.5.8.2, 4.5.8.3, and 4.5.8.4 for drug-specific delay guidance.

For each cohort, if the dose of one drug in the regimen (ie, pomalidomide, dexamethasone, nivolumab, or elotuzumab) is delayed, interrupted, or discontinued, the treatment with the other drugs may continue as scheduled. However, in the EPd cohort, if dexamethasone is delayed or discontinued discuss ongoing elotuzumab administration with the Medical Monitor. Subjects experiencing a 56 day delay in all study drugs due to an adverse event(s) related to study treatment must be discontinued from study drug. Subjects experiencing delays unrelated to study therapy, for example due to radiation therapy, may delay study treatment after discussion with the medical monitor.

Each cycle is 28 days. While dose delays or interruptions are permitted, the start of each cycle cannot be delayed and is fixed (ie, anchored) relative to Cycle 1 Day 1. Adjustments to the Cycle 1 Day 1 anchored schedule should not be performed. Missed doses should be skipped, not delayed, if not given within the allowed window.

Subjects may continue on study therapy even if components of the study therapy must be discontinued. For example, a subject may continue on study therapy if elotuzumab must be discontinued for an adverse event or other reason. Patients are considered still on study therapy even if they continue solely on pomalidomide, dexamethasone, or nivolumab.

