4.5.8.1 Dose Delay for Elotuzumab

In Cycles 1 to 2, elotuzumab doses that fall outside of the pre-specified window of -1 to +3 days must be skipped.

Beginning with Cycle 3 and beyond, elotuzumab dosing may be delayed for up to 1 week. If unable to administer within 1 week, then the dose should be skipped and resumption of the elotuzumab continues per the protocol defined schedule.

Subjects experiencing a Grade 4 infusion reaction related to elotuzumab must permanently discontinue elotuzumab.

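### SAP 7.4.1.10 ties dose-intensity periods to doses actually given, not to the protocol's fixed cycles, so a skipped Day 1 dose in the last cycle of a multi-dose period counts twice

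*SAP*

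**What the plan says.** SAP 7.4.1.10 defines dose intensity as 7 times the cumulative dose divided by the length of a period in days. Elotuzumab and dexamethasone have separate periods for Cycles 1 and 2 and for Cycle 3 onward; nivolumab has Cycles 1 to 4 and Cycle 5 onward; pomalidomide has one period.

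- **Start.** Each period starts at a dose actually given, for example "date of first dose of Elotuzumab in cycle 1".
- **End, elotuzumab Cycles 1 and 2.** The earliest of "date of first dose of Elotuzumab in the last cycle among the first 2 cycles+28, discontinuation date, death date".
- **End, nivolumab Cycles 1 to 4.** The earliest of "date of first dose of Nivolumab in the last cycle among the first 4 cycles+28, discontinuation date, death date".
- **End, pomalidomide.** The earliest of "date of first dose of Pomalidomide in the last cycle in which Pomalidomide was administered+28, discontinuation date, death date". This is the only formula that says which cycle counts as the last one.
- **Elotuzumab target.** "Planned dose per week for elotuzumab is 10mg/kg/week for the first 2 cycles, 5mg/kg/week for cycles 3 and beyond". The next sentence pools these: "The PDI per subject for elotuzumab will be computed by averaging the planned doses per week over the treatment duration".
- **Reporting.** RDI is tabulated in 10-point bands below 90%, down to under 60%.

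The protocol fixes the calendar. Section 4.5.8 says that "the start of each cycle cannot be delayed and is fixed (ie, anchored) relative to Cycle 1 Day 1", and that a dose not given within its window is skipped. Section 4.5.8.1 adds: "In Cycles 1 to 2, elotuzumab doses that fall outside of the pre-specified window of -1 to +3 days must be skipped". Section 4.5.4 has the same rule for nivolumab doses outside their window.

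**The concern.** The SAP's end date equals the end of the anchored cycle only when the first dose in the last cycle is given on Day 1. If that dose is skipped, the first dose given in the cycle is a later one. The period then runs past the cycle end by the same number of days, although the numerator has already lost the skipped dose. Two subjects who each miss one dose can get different RDIs and fall in different reporting bands, only because one of them missed Day 1.

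What is at stake is the accuracy of a descriptive exposure table. For a combination regimen, readers use that table to judge whether the planned treatment was delivered.

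**Working it through.** **Inputs.** Elotuzumab is 10 mg/kg on Days 1, 8, 15 and 22 of Cycles 1 and 2, then 20 mg/kg on Day 1 (Protocol 4.5.3). Nivolumab is 240 mg on Days 1 and 15 of Cycles 1 to 4, then 480 mg on Day 1 (Protocol 4.5.4). Targets are 10 then 5 mg/kg/week for elotuzumab and 120 mg/week for nivolumab (SAP 7.4.1.10). Days are counted from Cycle 1 Day 1 as day 0, so Cycle 2 ends at day 56 and Cycle 4 at day 112. C4D1 means Cycle 4 Day 1, and so on.

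**Formulas.** Dose intensity = 7 × cumulative dose / (end − start). RDI = dose intensity / target × 100%. The anchored comparison ends at the scheduled Day 1 of the last cycle + 28, with the same cap at discontinuation or death.

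**The plan's own figures.** Full dosing gives elotuzumab 7 × 80 / 56 = 10 mg/kg/week and nivolumab 7 × 1920 / 112 = 120 mg/week. Both match the SAP.

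**Skipped doses in a subject who continues treatment (elotuzumab target 10):**

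| Skipped | Dose given | SAP end (day) | SAP RDI | Anchored RDI |
|---|---|---|---|---|
| Nivolumab C4D15 | 1680 mg | 84 + 28 = 112 | 7 × 1680 / 112 = 105.0; 87.5% | 87.5% |
| Nivolumab C4D1 | 1680 mg | 98 + 28 = 126 | 7 × 1680 / 126 = 93.3; 77.8% | 87.5% |
| Elotuzumab C2D8 | 70 mg/kg | 28 + 28 = 56 | 7 × 70 / 56 = 8.75; 87.5% | 87.5% |
| Elotuzumab C2D1 | 70 mg/kg | 35 + 28 = 63 | 7 × 70 / 63 = 7.78; 77.8% | 87.5% |
| Elotuzumab C2D1 and C2D8 | 60 mg/kg | 42 + 28 = 70 | 7 × 60 / 70 = 6.0; 60.0% | 7 × 60 / 56 = 7.5; 75.0% |

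One skipped Day 1 dose costs 87.5 − 77.8 = 9.7 points too much and moves the subject down one band.

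**Overlap.** If the next period starts on time, days 56 to 63 (elotuzumab) or 112 to 126 (nivolumab) enter both denominators, while the dose that opens the next period is credited only there. For elotuzumab, those 7 days are charged at 10 mg/kg/week although the plan for them is 5.

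**When the effect vanishes.** With one cycle in the period, start and end move together and the length stays 28 days. For elotuzumab with C2D1 skipped, discontinuation or death by day 56 leaves no gap. At day 59 the gap is partial: 7 × 70 / 59 = 8.31, or 83.1% against 87.5%.

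**A delay with no missed dose.** From Cycle 3, Protocol 4.5.8.1 lets elotuzumab be given up to a week late. Over two such cycles with the second dose 7 days late, RDI is 7 × 40 / 63 = 4.44, or 88.9%. Over six cycles with the last dose late it is 7 × 120 / 175 = 4.8, or 96.0%. SAP 7.4.1.5 says delays within the window may be logistical and are not summarized.

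**Upward cases.**
- Elotuzumab from Cycle 3, four cycles, last dose omitted. If the last cycle means the last one dosed, RDI is 7 × 60 / 84 = 5.0, or 100%. Anchored, it is 7 × 60 / 112 = 3.75, or 75%. Nivolumab from Cycle 5 behaves the same way.
- Dexamethasone with C3D1 skipped, two cycles, equal weekly doses assumed: 7 weekly doses over 56 − 7 = 49 days give 100%, against 7/8 = 87.5%.

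**Pooled elotuzumab target.** For three cycles the SAP's example gives (40 + 40 + 20) / 12 = 8.33. One skip in Cycle 2 then gives 7.78 / 8.33 = 93.3% (Day 1) or 8.75 / 8.33 = 105% (Day 8). A fully dosed subject gets 10 / 8.33 = 120% in Cycles 1 and 2 and 5 / 8.33 = 60% in Cycle 3.

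**The case against.** Much can be said against a broad version of this point.

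- **Band change for elotuzumab.** A subject who reaches Cycle 3 has a pooled target below 10. At three cycles both one-skip results (93.3% and 105%) are at or above 90%, so no band changes. This stands, although the gap in points grows to 11.7 and two skips can still change band (6.0 / 8.33 = 72% against 7.5 / 8.33 = 90%). Nivolumab's target is a fixed 120 mg/week, so its band change does not depend on this.
- **Size.** A reader might infer a general understatement of 10 to 15 points. The documents do not support that. One elotuzumab skip costs 9.7 points; 15.0 needs two consecutive skips. A two-cycle nivolumab subject with C2D1 skipped would show 60.0% against 75.0%, and a 14-day pomalidomide hold at the start of the last of three cycles 66.7% against 77.8%. Both depend on the discontinuation date, which the SAP does not define: if it is the drug's own date, the cap can remove the gap. The effect also shrinks with longer treatment. The same pomalidomide hold in the last of 16 cycles costs 2.9 points.
- **Direction.** A reader might infer a systematic downward bias, because chemistry is scheduled only on Day 1. But in Cycles 1 and 2 blood counts are scheduled on all four dosing days (Tables 5.1-2 and 5.1-4), and Protocol 4.5.8.1 has no laboratory-based hold for elotuzumab. In EN Cycles 3 and 4 the blood count is scheduled on Day 1 only (Table 5.1-5), but that holds cluster there remains an inference. The upward cases also rule out a single direction.
- **Consequence.** The table is descriptive, and SAP 7.4.1.6 separately counts and lists omitted elotuzumab doses with reasons. This stands and limits the importance of the point.

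None of this removes the mismatch between a floating period and a fixed calendar.

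**Conclusion.** The point holds in a limited form. For a subject who continues treatment, with at least two cycles in the period and no discontinuation or death before the extended end date, a skipped Day 1 dose in the last cycle of a multi-dose period is counted twice. The cleanest case is nivolumab in Cycles 1 to 4, because it needs no assumption about the target. The elotuzumab percentages rest on a target of 10 mg/kg/week, which the SAP states for those cycles but then replaces with a pooled average.

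Outside that setting the floating dates can lower RDI with no dose missed, raise it, or leave the formula without a date to use. How many subjects are affected cannot be derived from the documents. PFS, ORR and their analyses are untouched. This is a minor correction, worth making because the stated rule gives equal exposure unequal RDI.

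**What to change.** In all dose-intensity formulas of SAP 7.4.1.10:

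1. Start each period at the scheduled Day 1 of its first cycle, and end it at the scheduled Day 1 of its last cycle + 28. Scheduled Day 1 is Cycle 1 Day 1 + 28 × (cycle number − 1). Keep the cap at discontinuation or death.
2. Define the last cycle as the last cycle on study treatment within that period, whether or not that drug was given in it.
3. State which discontinuation date applies, the drug's own or that of all study treatment. Subjects may stop one drug and continue the others, so items 2 and 3 must be read together.
4. Count crossover subjects' EPd cycles from their first EPd Day 1. Protocol Table 4.5-1 puts them on the schedule for Cycle 3 onward, but the documents do not say how their cycles are numbered.
5. Replace the pooled elotuzumab target with the period-specific ones already in the SAP: 10 mg/kg/week for Cycles 1 and 2, and 5 mg/kg/week from Cycle 3. Item 1 alone would leave a fully dosed three-cycle subject at 120% and 60%.

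The cost is a small edit to the SAP text and the derivation code. The inputs are Cycle 1 Day 1 and the cycle number, and the present formulas already need cycle numbers.

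### SAP 7.4.1.10 divides period-specific elotuzumab dose intensity by a planned intensity averaged over all cycles, so full dosing does not score 100% once a subject enters Cycle 3

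*SAP*

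**What the plan says.** The passage is SAP 7.4.1.10 (Cumulative Dose, Dose Intensity, and Relative Dose Intensity).

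- **Dose intensity.** "Elotuzumab dose intensity (mg/kg/week) per subject will be calculated separately for Cycles 1 and 2, and Cycle 3 and beyond". Two formulas follow, one per period. There is no formula for the whole of treatment.
- **Relative dose intensity (RDI).** Dose intensity divided by PDI, as a percentage. The sentence names no period.
- **Planned weekly dose.** "Planned dose per week for elotuzumab is 10mg/kg/week for the first 2 cycles, 5mg/kg/week for cycles 3 and beyond".
- **PDI.** "The PDI per subject for elotuzumab will be computed by averaging the planned doses per week over the treatment duration". The example, for a subject whose last dose opens Cycle 3, is (4×10 + 4×10 + 4×5)/12. The SAP prints the expression without evaluating it.
- **Reporting.** "The number and percentage of subjects whose relative dose intensity falls into the following categories will be presented". The bands are at least 90%, 80 to below 90%, 70 to below 80%, 60 to below 70%, and below 60%.

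**The concern.** An RDI should equal 100% when every planned dose is given on time. Here the numerator belongs to one period and the denominator to all of treatment. The planned weekly dose halves from 10 to 5 mg/kg at Cycle 3, so the averaged PDI lies between the two values. It is too small a divisor for Cycles 1-2 and too large for Cycle 3 onward. The two RDIs are then biased in opposite directions, and each depends on how long the subject stayed on treatment as well as on the doses received.

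What is at stake is the banded RDI table for elotuzumab, the investigational drug common to both cohorts. Fully dosed subjects could be tabulated as under-dosed in Cycle 3 onward, and under-dosed subjects as adequately dosed in Cycles 1-2.

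**Working it through.** **Inputs (SAP 7.4.1.10; schedule in SAP Table 2).** 10 mg/kg on Days 1, 8, 15 and 22 of Cycles 1 and 2; 20 mg/kg on Day 1 from Cycle 3; 28-day cycles. Assume every dose is given on schedule and k complete cycles, with k at least 3.

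**The SAP's own example.** (40 + 40 + 20)/12 = 100/12 = 8.33 mg/kg/week. It pools two cycles at 10 with one at 5, so a period-specific PDI cannot be read into the text.

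**Numerators.**
- Cycles 1-2: the "cumulative dose of Elotuzumab during the first 2 cycles" is 8 × 10 = 80 mg/kg over 56 days, so the intensity is 7 × 80/56 = 10 mg/kg/week.
- Cycle 3 onward: the "cumulative dose of Elotuzumab staring from Cycle 3" is 20(k−2) mg/kg over 28(k−2) days, so the intensity is 7 × 20/28 = 5 mg/kg/week.

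**Denominator.** PDI(k) = [2×10 + (k−2)×5]/k = 5(k+2)/k.

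**RDI as written.** Cycles 1-2: 10/PDI = 2k/(k+2). Cycle 3 onward: 5/PDI = k/(k+2).

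| Complete cycles k | PDI (mg/kg/week) | RDI, Cycles 1-2 | RDI, Cycle 3 onward |
|---|---|---|---|
| 3 | 8.33 | 120% | 60% |
| 4 | 7.50 | 133% | 67% |
| 6 | 6.67 | 150% | 75% |
| 12 | 5.83 | 171% | 86% |
| 17 | 5.59 | 179% | 89.5% |
| 18 | 5.56 | 180% | 90% |
| 24 | 5.42 | 185% | 92% |

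The limits as k grows are 200% and 100%. Setting k/(k+2) ≥ 0.9 gives k ≥ 18, so with 3 to 17 complete cycles a fully dosed subject is below the top band for Cycle 3 onward.

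**One or two cycles.** PDI = 10 and dose intensity = 10, so RDI = 100%; there is no Cycle 3 value.

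**Masking in Cycles 1-2.**
- 60% of planned dose, then 6 cycles in all: 6/6.67 = 90%, the top band.
- 50% of planned dose: 5/5.83 = 86% with 12 cycles, and 5/5.56 = 90% with 18.

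**Early stop within the last cycle.** The day count ends at the discontinuation or death date if that comes before the last cycle's 28 days are up.
- Stop 14 days after the Cycle 3 dose: 7 × 20/14 = 10; 10/8.33 = 120% for Cycle 3 onward.
- Stop 14 days after the Cycle 12 dose: 7 × 200/(9×28 + 14) = 1400/266 = 5.26; 5.26/5.83 = 90.2%.

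**After correction (complete cycles).** Period-matched PDIs give 10/10 and 5/5, which is 100% in both periods for every k. An overall dose intensity, 7 × [80 + 20(k−2)]/(28k), reduces to 5(k+2)/k. That is the averaged PDI, so the ratio is again 100%.

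**The case against.** The best reply is that only dose intensity is said to be calculated by period. The RDI sentence is singular, the PDI is per subject, and the band table counts subjects. All this suggests one RDI per subject, with the averaged PDI meant for an overall dose intensity; full dosing would then score 100%. The planned values and the worked example are also correct in themselves. This is a plausible account of the intent, but it does not rescue the text: no overall elotuzumab dose intensity is defined, and the only formulas available to a programmer are the two period-specific ones.

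The reply that the harm is limited stands. Period-specific dose intensity is itself summarised and can be read against the stated 10 and 5 mg/kg/week. Omissions are tabulated separately (SAP 7.4.1.6), and fully dosed subjects at 120% or more would probably prompt a query. No endpoint, sample size or stopping rule uses RDI.

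Three stronger inferences are tempting, and the documents do not support them:
- **That every subject is affected.** Those with one or two cycles are not.
- **That a fully dosed subject cannot reach the top band for Cycle 3 onward before 18 cycles.** This holds only for complete cycles; the early-stop examples give 120% and 90.2%.
- **That RDI is the main exposure measure.** The SAP does not say so, and its topline list (SAP 9.1) has number of cycles as the only exposure item.

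**Conclusion.** The mismatch is real as written. For any subject treated into Cycle 3 or later with complete 28-day cycles, full dosing scores 2k/(k+2) and k/(k+2) instead of 100%. The size depends on k, so no single range applies to all subjects. These figures assume every dose on schedule and complete cycles; stopping partway through the last cycle moves the Cycle 3 value upward.

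The problem is specific to pairing the averaged elotuzumab PDI with split intensities. Nivolumab intensity is also split by period, but its planned 120 mg/week fits both periods (2×240/4 and 480/4). Pomalidomide uses one intensity and one planned value, 21 mg/week. The consequence is confined to descriptive exposure tables. It should be corrected before those tables are programmed, but it has no bearing on the efficacy results.

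**What to change.** State in SAP 7.4.1.10 that elotuzumab RDI is reported by period, with PDI 10 mg/kg/week for Cycles 1-2 and 5 mg/kg/week for Cycle 3 onward, and label the band table by period. If one RDI per subject is wanted, instead of or in addition to these, define an overall dose intensity (total mg/kg over the whole treatment interval) and divide that by the averaged PDI.

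Neither change removes the effect of an early stop, because that comes from the day count in the dose intensity formula. A footnote to the table would cover it.

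The cost is a few words of SAP text and one derivation. No new data are needed, and the treatment schedule is not touched.

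### The dose-intensity formulas cut the observed clock at discontinuation or death but compare it with a full-cycle planned rate, so mid-cycle stops inflate the exposure figures

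*SAP*

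**What the plan says.** SAP 7.4.1.10 gives each drug's dose intensity as 7 times the cumulative dose divided by a number of days. The days run from the first dose in the period to the earliest of three dates: 28 days after the first dose of the last cycle, discontinuation, or death. No day is added. Pomalidomide: "7x[cumulative dose of pomalidomide / (min(date of first dose of Pomalidomide in the last cycle in which Pomalidomide was administered+28, discontinuation date, death date"). Elotuzumab from Cycle 3: "7x[cumulative dose of Elotuzumab staring from Cycle 3 / (min(date of first dose of Elotuzumab in the last cycle+28, discontinuation date, death date"). Nivolumab from Cycle 5: "7x[cumulative dose of Nivolumab staring from Cycle 5 / (min(date of first dose of Nivolumab in the last cycle+28, discontinuation date, death date"). Dexamethasone and the earlier cycles of elotuzumab and nivolumab follow the same pattern.

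The numerator is dose actually given; for pomalidomide it is "the sum of each dose they took, as recorded in their medication diary".

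The planned rates are cycle averages. Pomalidomide follows "the standard daily dose, 4 mg from Day 1 to Day 21 during each cycle", giving a "planned dose intensity per week, 21mg times 100"%. Nivolumab uses 120 mg/week. For elotuzumab, "Planned dose per week for elotuzumab is 10mg/kg/week for the first 2 cycles, 5mg/kg/week for cycles 3 and beyond"; these rates are then averaged over the subject's treatment duration. The SAP's worked example, for a subject whose last dose is the first of Cycle 3, is (4 × 10 + 4 × 10 + 4 × 5)/12.

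Dose intensity is reported with mean, SD, median, quartiles, minimum and maximum. For RDI, "The number and percentage of subjects whose relative dose intensity falls into the following categories will be presented"; the top band is ≥ 90%, with no upper limit.

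**The concern.** The observed rate and the planned rate cover different intervals. The planned rate spreads the cycle's dose over all 28 days, including days when nothing is due. The observed rate loses those days as soon as discontinuation or death comes before day 28. The schedules put the dose early in the cycle: Day 1 only for elotuzumab from Cycle 3 and nivolumab from Cycle 5, and Days 1-21 for pomalidomide (Protocol Tables 4.5-1 and 4.5-2). A mid-cycle stop can therefore score above 100% with no excess dosing.

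Two gaps make this worse. The formulas omit the extra day that SAP 7.4.1.1 and 8.2 use for durations, so a stop on the first dosing day leaves a zero denominator. The discontinuation date is also undefined: it could be the single drug or all study treatment, although Protocol 4.5.8 and SAP 7.4.4 both allow drugs to stop separately.

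At stake are the mg/week summaries, where one extreme value can dominate a small cohort, and the RDI category of subjects who reduced or missed doses before a mid-cycle stop.

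**Working it through.** **The plan's own rates, reproduced**
- Pomalidomide: 4 mg × 21 / 4 weeks = 21 mg/week.
- Nivolumab: 2 × 240 / 4 = 480 / 4 = 120 mg/week.
- Elotuzumab from Cycle 3: 20 / 4 = 5 mg/kg/week; worked example 100 / 12 = 8.33 mg/kg/week.
- A complete pomalidomide cycle run to day 28: 7 × 84 / 28 = 21 mg/week, or 100%.

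So the formula is correct when the clock is not cut short.

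**Mid-cycle stops**

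RDI = 7 × dose / days from first dose to stop / planned rate. All due doses are taken, and the stop date is that of the individual drug.

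| Case | Calculation | RDI |
|---|---|---|
| Nivolumab 480 mg at Cycle 5 Day 1, stop at 7 days | 7 × 480 / 7 / 120 | 400% |
| Same, 14 days | 7 × 480 / 14 / 120 | 200% |
| Same, 21 days | 7 × 480 / 21 / 120 | 133% |
| Pomalidomide 4 mg × 21, stop Day 22 of Cycle 1 | 7 × 84 / 21 / 21 | 133% |
| Pomalidomide, stop Day 21 of Cycle 2 | 7 × 168 / 48 / 21 | 117% |
| Pomalidomide, stop Day 21 of Cycle 12 | 7 × 1008 / 328 / 21 | 102% |
| Elotuzumab 20 mg/kg at Cycle 3 Day 1, stop at 7 days, averaged rate 8.33 | 7 × 20 / 7 / 8.33 | 240% |
| Same, 14 days | 7 × 20 / 14 / 8.33 | 120% |
| Same, 21 days | 7 × 20 / 21 / 8.33 | 80% |

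The elotuzumab cases become 400%, 200% and 133% only if the planned rate is taken as 5. Without truncation the averaged rate would give 7 × 20 / 28 / 8.33 = 60%, so even the 80% is inflated. Setting a Cycle 3 dose intensity against a rate averaged over all cycles is a separate matter.

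**First-day stop.** Days = 0, so the result is undefined for every drug. Adding one day removes the zero but not the inflation: a Day 21 pomalidomide stop gives 7 × 84 / 21 / 21 = 133%, and a full cycle drops to 7 × 84 / 29 / 21 = 96.6%.

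**Category shifts (pomalidomide)**
- 3 mg × 21, stop Day 22 of Cycle 1: 7 × 63 / 21 / 21 = 100%, against 63 / 84 = 75% of scheduled dose.
- 4 mg in Cycle 1, then 3 mg in Cycles 2-6, stop Day 22 of Cycle 6: dose 84 + 5 × 63 = 399 mg over 161 days. This gives 7 × 399 / 161 / 21 = 82.6%, against 399 / 504 = 79.2%. The subject moves from the 70% to < 80% band to the 80% to < 90% band.

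**Effect on a mean.** A stop one day after nivolumab 480 mg gives 7 × 480 / 1 = 3,360 mg/week. As an illustration, with 29 other subjects at exactly 120, the mean is (29 × 120 + 3,360) / 30 = 228 mg/week.

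**Undefined date.** Take a subject who stops pomalidomide after seven doses (28 mg). With a drug-specific date on Day 8, RDI is 7 × 28 / 7 / 21 = 133%. If the date means all study treatment and the other drugs continue past day 28, it is 7 × 28 / 28 / 21 = 33%.

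**The case against.** The best defence is that little of this reaches the RDI table. The top band is open, so 400%, 133% and 100% fall in the same cell. Subjects who took every dose due stay at 90% or above under any sensible correction. That stands: only subjects who both reduced or missed doses and stopped mid-cycle can change category.

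Real reductions are also visible elsewhere. SAP 7.4.1.6 and 7.4.1.8 tabulate elotuzumab omissions and pomalidomide reductions, and cumulative dose and number of cycles are summarised. The RDI categories are therefore not the only record of reductions.

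Frequency is unknown. Response is assessed every 4 weeks on Day 1, so a progression stop dated at that visit falls close to day 28, where truncation has little or no effect. If the discontinuation date means all study treatment, a subject who stops elotuzumab on the day of a Grade 4 infusion reaction but continues pomalidomide and dexamethasone (Protocol 3.5) has no same-day stop. Both points limit the size. Neither removes the problem, because death cuts the clock under any reading and the SAP does not say which date applies.

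A reader might infer that early stoppers generally score 130-400%. They do not. That range fits one 4-weekly dose stopped 21 to 7 days later at a planned rate of 120 mg/week, or 5 mg/kg/week for elotuzumab. Under planned dosing pomalidomide peaks at 7 × 8 / 1 / 21 = 267% (stop on Day 2) and falls towards 100% with later cycles. Nor is 400% a ceiling: a next-day stop after a 4-weekly dose gives 2,800% at those same rates. A heavier effect in the EN cohort is plausible, but the documents give no exposure figures to support it.

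**Conclusion.** The formulas are wrong as written for any subject who stops a drug or dies less than 28 days after the first dose of the last cycle. The inflation is large for a single 4-weekly infusion (133-400% for nivolumab at 21 to 7 days) and modest for pomalidomide after the first cycle (about 102-117%). The mg/week mean, SD and maximum are distorted, some RDI categories are too high, and a first-day stop cannot be computed.

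The figures assume dosing as planned, except in the reduced-dose examples, and a stop date specific to the drug. How many subjects are affected cannot be judged from the documents. It does not follow that early stoppers are wrongly counted at 90% or above: those who took every due dose belong there on a dose-due basis. Only descriptive exposure tables are affected. This should be corrected before those tables are produced, but it does not bear on PFS, ORR or OS.

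**What to change.** In SAP 7.4.1.10:

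1. Define the discontinuation date in these formulas as the date the individual drug was stopped.
2. Compute mg/week (mg/kg/week for elotuzumab) over whole 28-day cycles started: first dose of the last cycle + 28, minus first dose in the period, with no cut at discontinuation or death. The nivolumab examples then give 7 × 480 / 28 = 120 mg/week.
3. Compute RDI for each drug as cumulative dose received divided by the dose scheduled under the protocol from first dose to the earliest of discontinuation, death, or the end of the last cycle in which the drug was given. This keeps the existing 28-day cap, so a stop recorded after a long delay does not add scheduled doses. Always count the first scheduled dose, so that the denominator is above zero, and state whether a dose due on the stop date counts.

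The full-dose examples then score 100%, and the two reduced-dose examples 75% and 79.2%.

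The cost is SAP wording and a small programming change, with no new data. Slightly fewer subjects will fall in the higher RDI bands. RDI will also no longer equal dose intensity divided by planned dose intensity, so the SAP should say so.
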